## 6.9 Antiemetic Therapy

If a subject experiences nausea and/or vomiting, the subject may be given prophylactic antiemetics treatment prior to the next dose of NKTR-102. The subject must be carefully monitored throughout the study period, and given adequate fluid and electrolyte replacement to prevent dehydration and electrolyte imbalance.

## 6.10 Use of Growth Factor Support and Transfusions

Upon NKTR-102 administration, subjects may experience neutropenia. Subjects who do not meet retreatment criteria for ANC should return to clinic within 3-7 days for reassessment. If the subject continues not to meet retreatment criteria for ANC, she should return to clinic at weekly intervals for reassessment. Subjects must demonstrate an ANC  $\geq 1.5 \times 10^9/L$  prior to retreatment with NKTR-102.

Prophylactic use of growth factor support is not permitted, however use of growth factor support in a setting of neutropenia is permitted. Use of growth factor support must follow American Society Clinical Oncology (ASCO), European Society for Medical Oncology (ESMO) guidelines or standard of care at the local institution. For example, if a subject required growth factor support during a previous cycle, a subject may be administered prophylactic growth factor support during a subsequent cycle at the investigator's discretion.

Subjects may receive transfusions (platelets or blood products) at the Investigator's discretion.

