Dose reductions may also be implemented for subjects who experience recurrent or specific severe toxicities (see [Table 4](#)). NKTR-102 doses for an individual subject may be reduced by 25 mg/m^2 based on conditions listed in [Table 4](#). Subjects should be discontinued from the study treatment if toxicity would indicate more than 2 dose reductions. Dose re-escalation for NKTR-102 is not permitted.

- For subjects entering this study at a starting dose of 145 mg/m^2: dose reductions to 120 mg/m^2, then to 95 mg/m^2 may occur based on conditions listed in [Table 4](#).
- For subjects (i.e., from Protocol 12-102-13) entering this study at a starting dose of 120 mg/m^2: dose reductions to 95 mg/m^2, then to 70 mg/m^2 may occur based on conditions listed in [Table 4](#).
- For subjects (i.e., from Protocol 12-102-13) entering this study at a starting dose of 95 mg/m^2: dose reduction to 70 mg/m^2 may occur based on conditions listed in [Table 4](#).
- For subjects (i.e., from Protocol 12-102-13) entering this study at a starting dose of 50 mg/m^2: dose reduction should be approved by Medical Monitor.
- [Table 4](#) provides instructions regarding dose modification.
- DURING A CYCLE: [Table 4](#)/Column 2 describes the recommended guidelines for management and supportive care during a cycle of therapy.
- INITIATION OF A SUBSEQUENT CYCLE: [Table 4](#)/Column 3 describes the recommended dose modifications for Day 1 in subsequent cycles of therapy. All dose modifications in a new cycle should be based on the worst toxicity observed in the previous cycle and the dose reduction will be relative to the Day 1 dose of the previous cycle.

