**Table 4: NKTR-102 Dose Modifications**

Toxicity NCI CTCAE Grade	During a Cycle	Dose Modifications for Day 1 of New Cycle
Neutropenia / Febrile Neutropenia		
Grade 1 (ANC <1500/mm  )		Maintain dose level.
Grade 2 (ANC ≥1000/mm  , <1500/mm  )	Consider growth factor support in accordance with local guidelines.	
If present on a treatment day, hold therapy until toxicity resolves to ANC ≥1500/mm^3.
 
 
• ↓ 1 dose level after 1st occurrence (provided screening ANC > 2000/mm^3); do not reduce dose for Grade 2 neutropenia if screening ANC was ≥ 1500 and < 2000/mm^3. Consider prophylactic growth factor therapy.
 
• ↓ 1 dose level after 2nd occurrence. Consider prophylactic growth factor therapy.
 
 
Provided that adequate supportive care has been given to the patient, and the investigator believes it is in the best interest of the patient, retreatment may be attempted for a 3rd episode of Grade 2 ANC.

Grade 3 (ANC ≥500/mm  , <1000/mm  )	Consider growth factor support in accordance with local guidelines.	
If present on a treatment day, hold therapy until toxicity resolves to ANC ≥ 1500/mm^3.
 
 
• ↓ 1 dose level after 1st occurrence. Use prophylactic growth factor therapy.
 
• ↓ 1 dose level after 2nd occurrence. Use prophylactic growth factor therapy.
 
 
Provided that adequate supportive care has been given to the patient, and the investigator believes it is in the best interest of the patient, retreatment may be attempted for a 3rd episode of Grade 3 ANC.

Grade 4 (ANC <500/mm  )	Consider growth factor support in accordance with local guidelines. Consider use of antibiotic (oral fluoroquinolones) even in the absence of fever or diarrhea.	
If present on a treatment day, hold therapy until toxicity resolves to ANC ≥ 1500/mm^3.
 
 
• ↓ 1 dose level after 1st occurrence. Use prophylactic growth factor therapy.
 
• ↓ 1 dose level after 2nd occurrence. Use prophylactic growth factor therapy.
 
 
Discontinue NKTR-102 after 3rd occurrence.

Toxicity NCI CTCAE Grade	During a Cycle	Dose Modifications for Day 1 of New Cycle

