Febrile Neutropenia Grade 3 or 4 (ANC <1000/mm  with a single temperature of ≥ 38.3°C (101°F) or a sustained temperature of ≥ 38°C (100.4°F) for more than one hour	Treat as appropriate (eg, growth factor support; antibiotics); consider hospital admission. Patients should be hospitalized for IV antibiotic therapy if sepsis is suspected.	Retreatment must be delayed until the toxicity is Grade ≤ 1. 
 
• ↓ 1 dose level after 1st occurrence. Use prophylactic growth factor therapy.
 
• ↓ 1 dose level after 2nd occurrence. Use prophylactic growth factor therapy.
 
 Discontinue NKTR-102 after 3rd occurrence.
Thrombocytopenia		
Grade 1 or 2		Maintain dose level.
Grade 3 (Platelets ≥ 25, <50K)	Consider platelet transfusion if active bleeding. Following platelet transfusion, retreatment must be delayed for 7 days and patient must meet retreatment criteria prior to dosing.	If present on a treatment day, hold therapy until toxicity resolves to platelets ≥ 50K. 
 
• ↓ 1 dose level after 1st occurrence.
 
• ↓ 1 dose level after 2nd occurrence.
 
 Provided that adequate supportive care has been given to the patient, and the investigator believes it is in the best interest of the patient, retreatment may be attempted for a 3rd episode of Grade 3 thrombocytopenia.
Grade 4 (Platelets < 25K)	Consider platelet transfusion if platelets ≤10K or with active bleeding. Following platelet transfusion, retreatment must be delayed for 7 days and patient must meet retreatment criteria prior to dosing.	If present on a treatment day, hold therapy until toxicity resolves to platelets ≥ 50K. 
 
• ↓ 1 dose level after 1st occurrence.
 
• ↓ 1 dose level after 2nd occurrence.
 
 Discontinue NKTR-102 after 3rd occurrence.
Anemia		
Grade 1 or 2		Maintain dose level

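### Section 6.10 does not permit prophylactic growth factor, while Table 4 says to use it after Grade 3, Grade 4 or febrile neutropenia; read literally, they conflict when the event was managed without growth factor

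*Protocol*

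**What the plan says.** Protocol Section 6.10 gives a general rule: "Prophylactic use of growth factor support is not permitted, however use of growth factor support in a setting of neutropenia is permitted". It then ties growth factor use to ASCO or ESMO guidelines or the local standard of care, and adds an illustration: "For example, if a subject required growth factor support during a previous cycle", then "a subject may be administered prophylactic growth factor support during a subsequent cycle at the investigator's discretion". The same section requires an ANC of at least 1.5 x 10^9/L before retreatment.

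Protocol Table 4 covers the same subject in two columns.

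- During the cycle, for Grade 2, 3 and 4 neutropenia: "Consider growth factor support in accordance with local guidelines". For febrile neutropenia: "Treat as appropriate (eg, growth factor support; antibiotics", so growth factor is one example of treatment.
- On Day 1 of the new cycle, after a first or second Grade 3, Grade 4 or febrile event: "Use prophylactic growth factor therapy". After Grade 2, prophylaxis is only to be considered.

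Section 6.7 introduces the new-cycle column as one that "describes the recommended dose modifications for Day 1 in subsequent cycles of therapy". The neutropenia rows of Table 4 do not refer to Section 6.10, Section 6.10 does not refer to Table 4, and no text says which governs.

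**The concern.** An investigator planning the cycle after a Grade 3, Grade 4 or febrile event can find two instructions. One says prophylaxis is not permitted outside a narrow example; the other says to use it. A site that follows Section 6.10 to the letter would withhold growth factor that a site following Table 4 would give.

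What is at stake is patient safety and uniform conduct across as many as 100 sites. Section 2.1.2.4 warns that neutropenia accompanied by severe diarrhea, dehydration, fever and infection can progress to sepsis and death. No planned calculation depends on this point: the SAP (Section 6.1) requires no hypothesis test and no specific sample size, and Protocol Section 12.2 plans only descriptive safety summaries.

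**Working it through.** The main check is a comparison of text, case by case.

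| Situation before the next cycle | Section 6.10 | Table 4, new cycle | Result |
|---|---|---|---|
| No earlier neutropenia | Not permitted | Silent | No conflict |
| Grade 2, growth factor given | Allowed at discretion | Consider | Compatible |
| Grade 2, growth factor not given | Example does not apply | Consider | Unclear, but nothing is directed |
| Grade 3, Grade 4 or febrile, growth factor given | Allowed at discretion | Use | Differ in force only |
| Grade 3, Grade 4 or febrile, growth factor not given | Example does not apply; literal bar stands | Use | Literal conflict |

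The last row is a path that complies with the protocol, because the during-cycle column makes growth factor optional for each of these events.

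Does the allowance for use in a setting of neutropenia remove the conflict? Not clearly. Retreatment waits until ANC is at least 1.5 x 10^9/L, so at the start of the next cycle the subject has recovered to that threshold. The clause may cover prophylaxis given then, but it need not.

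For size, the documents give no count of events managed without growth factor, so only an upper reference can be formed. The inputs are:

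- Enrolment ceiling: 150 (Protocol synopsis).
- Phase 3 BEACON rates of Grade 3 or higher neutropenia: 7.5% (Section 2.1.2.4) and 9.6% (Section 2.1.2.5). The protocol does not explain the difference.
- Table 1 neutropenia row: Grade 1, 2.1%; Grade 2, 11.8%; Grade 3, 5.4%; Grade 4, 2.1%.

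Reproducing the plan's own total: 2.1 + 11.8 + 5.4 + 2.1 = 21.4%, as printed. Grade 3 plus Grade 4: 5.4 + 2.1 = 7.5%, which agrees with Section 2.1.2.4.

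Expected subjects = 150 x rate:

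- Grade 3 or higher at 7.5%: 150 x 0.075 = 11.25
- Grade 3 or higher at 9.6%: 150 x 0.096 = 14.4
- Of the 11.25: Grade 3, 150 x 0.054 = 8.1; Grade 4, 150 x 0.021 = 3.15
- Grade 2, where Table 4 says only to consider: 150 x 0.118 = 17.7

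The 11 to 14 are all subjects with a Grade 3 or higher event. Those in literal conflict are the part whose event was managed without growth factor, and that share is unknown.

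**The case against.** The strongest reply is that the conflict comes from reading one sentence of Section 6.10 apart from its paragraph. The paragraph itself allows prophylaxis in a later cycle, so the bar cannot be absolute. It defers to ASCO or ESMO guidelines or local practice, and its illustration opens as an example, so it does not list every allowed case. Section 6.11 permits whatever supportive care is needed, and the prohibited list in Section 6.11.2 does not name growth factor. Taken together, the protocol would mean no primary prophylaxis, with Table 4 governing after an event.

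Much of this stands: it is probably what was intended. A reader might infer that the protocol imposes a blanket ban that Table 4 flatly contradicts. The documents do not support that. What survives is narrower: the intended reading is not written down, and the one example given depends on growth factor having been needed earlier. Nor can a site assume that Table 4 always reflects the section text. Section 6.8 forbids prophylactic antidiarrheals, yet Table 4 calls for them after Grade 2 or worse diarrhea.

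A reader might also infer that Section 11.1, which restricts deviations, pushes sites toward withholding. It cuts both ways: Table 4 is also protocol text, and the section excepts action against immediate hazards. Finally, a reader might infer that neutropenia in the original study should count toward secondary prophylaxis. Section 6.5 deals with carrying forward reduced doses, not with growth factor, so such a rule would be a new clinical decision.

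**Conclusion.** The point holds as a wording conflict on one compliant path: a first or second Grade 3, Grade 4 or febrile event managed without growth factor. Where growth factor was given, the texts differ only in strength. It is worth correcting because the toxicity can be fatal and sites could reasonably act in different ways.

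The subset affected is unknown, and is at most roughly 11 to 14 subjects. That ceiling assumes that all 150 subjects enrol and that the Phase 3 rates carry over to this previously treated population; the true rate could be higher or lower. It would be wrong to read 11 to 14 as the number who would be denied prophylaxis or harmed.

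The consequence is also limited by rules that apply on either reading. For neutropenia on a treatment day, Table 4 says "If present on a treatment day, hold therapy until toxicity resolves to ANC" of at least 1500/mm3; after febrile neutropenia, retreatment waits for Grade 1 or lower. The dose falls one level after each of the first two Grade 3, Grade 4 or febrile events, and the drug stops after a third Grade 4 or febrile event. Section 6.10 adds an ANC recheck at 3 to 7 days and then weekly.

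**What to change.** Amend Section 6.10 only. State that primary prophylaxis is not permitted. State that secondary prophylaxis after neutropenia follows Table 4 (use after Grade 3, Grade 4 or febrile neutropenia; consider after Grade 2), in line with ASCO, ESMO or local guidelines, whether or not growth factor was given during the event. Align the example sentence with this, so that investigator discretion does not undercut Table 4. Whether neutropenia in the original study counts is for the sponsor to decide.

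The cost is one or two sentences in the next protocol amendment, with the IRB/IEC approval that Section 13.1 requires for amendments. Table 4's neutropenia rows and the SAP need no change.

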## 6.11 Prior and Concomitant Medications

Throughout the study, Investigators may prescribe any concomitant medications or treatments deemed necessary to provide adequate supportive care.

All medications (both prescription and over-the-counter [OTC] medications), vitamin and mineral supplements, and/or herbs taken by the subject from Screening through the End-of-Treatment visit will be documented on the concomitant medication eCRF. Throughout the study, Investigators may prescribe any concomitant medications or treatments deemed necessary to provide adequate supportive care. All concomitant medications administered to study subjects will be recorded in the eCRF.

### 6.11.1 Permitted Treatments

- Palliative and supportive care for disease-related symptoms.
- Standard therapies for concurrent medical conditions, including antiemetic prophylaxis (see Section 6.9) and early interventional antidiarrheal therapy (see Section 6.8).
- Diarrhea is an expected toxicity of NKTR-102. All subjects must receive optimal antidiarrheal therapy immediately after the FIRST episode of diarrhea or loose stool regardless of severity.
- Premedication with antihistamine and/or corticosteroid is allowed in subsequent cycles following occurrence of a self-limiting allergic/hypersensitivity reaction to a prior infusion of NKTR-102.

### 6.11.2 Prohibited Concomitant Medications

The treatments listed below are prohibited while on study. For treatments prohibited on study, alternative medical intervention should be considered; if a prohibited treatment is required, study drug treatment should be discontinued.

- Any concurrent chemotherapy (other than NKTR-102), radiotherapy (with the exception of palliative radiation), biological therapy, hormonal agents used for the treatment of cancer, immunotherapy, or other systemic therapy for cancer; megestrol acetate for appetite stimulation may be used;
- Other investigational agents within 28 days prior to Day 1 of Cycle 1 or during the study;

- Investigators must monitor subjects for use of potent cytochrome P450 3A4 (CYP3A4) inducers or inhibitors, as they may induce or inhibit irinotecan or SN38 metabolism. Some of these agents are OTC medications (e.g., St John's Wort); subjects must provide a complete list of all concomitant medications as part of the screening process. See [Appendix 2](#) for a list of agents known to induce and inhibit CYP3A4.

### 6.11.3 Adequate Forms of Birth Control

Over the course of the study, women of childbearing potential (WCBP) and men must agree to use adequate contraception during study participation (at least two methods of contraception, one of which includes a barrier method [male condom] by the male partner or abstinence) or a male who has undergone a vasectomy greater than 6 months prior to Cycle 1 Day 1. Women of childbearing potential are women who are not 2 years postmenopausal or are not surgically sterile.

Protections against pregnancy should be continued for at least 8 months after the last dose of NKTR-102.

## 7.0 EVALUATIONS BY VISIT

A summary of study assessments and procedures are shown in the Schedule of Assessments ([Appendix 1](#)). Laboratory evaluations prior to treatment in this study will be done at local laboratories. Each laboratory must be certified and must be listed on the Statement of Investigator Form FDA 1572.

### 7.1 Screening

The following procedures will be performed for all potential subjects at a screening visit conducted within 28 days prior to Cycle 1 Day 1. Any procedures, as applicable, that were completed as part of the end-of-study visit for the original protocol may be used and do not need to be repeated if they were performed within 7 days of Cycle 1 Day 1 of this extension study. The maximum delay between treatment with the last dose of NKTR-102 and treatment with NKTR-102 in this study is 8 weeks.

- Informed consent by subject or subject's legal representative
- Medication history (including previous chemotherapy, radiation, treatment with biologics, OTC drugs, herbs and St. John's Wort)
- Demographics including birth date, race/ethnicity, and gender at birth
- Complete physical examination, including height and body weight and vital signs (pulse, temperature, and blood pressure)
- ECOG performance status
- Serum pregnancy test (WCBP only)
- Disease assessment with computed tomography (CT), magnetic resonance imaging (MRI) scanning, or digital photography, unless subject had disease assessment within 8 weeks prior to treatment in the Extension study
- Hematology and serum chemistry: minimally required are hemoglobin, ANC, platelets, and creatinine. Complete blood count (CBC) and other laboratory tests will be obtained at the discretion of the Investigator.
- Assessment of AEs (see Section [9.2](#) for details on AE collection from the time of the original protocol to the start of the Extension study)

## 7.2 Treatment Days

For all cycles, safety assessments are required before each treatment cycle. All results must be available before dosing. For all cycles, Day 1 assessments may be performed up to 5 days before Day 1. The following procedures will be performed prior to each dose:

- Symptom-directed physical examination, including body weight
- ECOG performance status
- Vital signs (pulse, temperature, blood pressure)
- Hematology and serum chemistry: minimally required are hemoglobin, ANC, platelets, and creatinine. Complete blood count and other laboratory tests will be obtained at the discretion of the Investigator.
- Body surface area
- Urine pregnancy test (only for WCBP)
- Assessment of concomitant medications
- Assessment of AEs
- Diarrhea must be fully resolved to NCI-CTCAE Grade 0 (a return to normal bowel movement habits) for at least 7 days without supportive antidiarrheal measures prior to treatment. Any treatment-related non-hematologic toxicities must have resolved to baseline or Grade 1
- NKTR-102 for Injection administration

**NOTE:** Disease assessment (tumor response and progression assessments) should be performed as per local standard of care. Best response and date of progression will be collected in this protocol. Other procedures and evaluations may be performed as clinically indicated and as determined by the investigator.

All safety laboratory evaluations will be performed at a local laboratory. Each laboratory must be certified and must be listed on the Statement of Investigator Form FDA 1572.

## 7.3 End-of-Treatment Visit

The End-of-Treatment visit is to occur 30 days ( $\pm$  7 days) after last dose of study drug.

The following procedures will be performed for all subjects at the end of the subject's treatment:

- Complete physical examination, including body weight
- ECOG performance status
- Vital signs (pulse, temperature, blood pressure)
- Urine pregnancy test (only for WCBP)
- Assessment of concomitant medications
- Assessment of AEs

#### **7.4 Quarterly Follow-up**

Approximately every 12 weeks ( $\pm 4$  weeks) following the End-of-Treatment visit, subjects will have their medical records reviewed and may be contacted to assess disease status, survival status, receipt of subsequent anti-cancer therapy, and resolution of all toxicity attributable to study drug. Disease status during follow-up will only be assessed if the subject has not demonstrated disease progression since receiving NKTR-102. Quarterly follow-up will continue until death, withdrawal of consent by subject, physician decision, lost to follow-up, or the study is terminated by the Sponsor.

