### 4.2 Study Design

[figure not shown]
This is a multicenter, open-label, Phase 2 study of NKTR-102 in subjects with solid tumors who received NKTR-102 in a prior Nektar-sponsored clinical study. Following completion of NKTR-102 treatment on a prior NKTR-102 clinical study, subjects will be assessed for eligibility. The Sponsor must assess eligibility criteria prior to enrollment of all subjects.

Eligible subjects will continue treatment with NKTR-102 at a dose of 145 mg/m^2 or less in a q21d schedule as outlined in Section 6.5. Subjects who previously received a dose of NKTR-102 at <145 mg/m^2 will continue at the lower dose in this study. Subjects who underwent dose reduction of NKTR-102 due to observed toxicity prior to participation in the Extension study (Protocol 11-PIR-09) will not be re-escalated to the previous dose level upon resolution of the toxicity. Dose escalation for NKTR-102 is not permitted.

NKTR-102 will be administered as an IV infusion over approximately 90 minutes ( $\pm$  15 minutes) on Day 1 of each 21-day treatment cycle. Disease assessments for tumor response and progression will be performed as per local standard of care until disease progression. Minimal disease evaluation data (best response and date of progression) will be collected within this protocol. Tumor measurements are not required; only an overall assessment of response or progression by the Investigator is required. Subjects may continue to receive repeated cycles of NKTR-102 on this protocol as long as there is evidence of disease control in the judgment of the Investigator or until there is unacceptable toxicity, death, withdrawal of consent by the subject, Investigator decision, subject non-compliance, lost to follow-up or study is terminated by the Sponsor. After discontinuation of NKTR-102, all subjects, except those who withdraw consent from further study follow-up, are to be followed for disease status (as applicable), subsequent anti-cancer therapy, survival status, and resolution of toxicity attributable to study drug (with contact by phone, through a clinic visit, or through review of medical records approximately every 12 weeks ( $\pm$  4 weeks)).

A schematic of the study design is presented in [Figure 1](#).

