### 5.3 Early Withdrawal/Discontinuation from Study

Subjects may choose to discontinue/withdraw from study drug treatment or the study at any time, for any reason, and without prejudice to further treatment. A subject who withdraws consent from study participation will be asked to state the level of withdrawal:

1. Withdrawal from treatment only; and/or
2. Withdrawal from contact during the post-treatment period (for off-study data, such as subsequent anti-cancer therapy or survival).

In the event of withdrawal of consent, the study staff and/or Investigator must make every effort to ascertain the level of consent withdrawn. An objective of this study is to assess survival status, so site personnel must ascertain if subjects will permit continued follow-up if consent is withdrawn. The type of consent withdrawal must be noted in source documents and CRF.

Subjects may stop NKTR-102 treatment or be withdrawn from the study for any of the following reasons, but will be followed for safety until resolution or permanent sequelae of all toxicities attributable to NKTR-102 (see Section 9.5):

- Progression of disease
- Adverse Event (unacceptable toxicity)
- Death
- Non-compliance of the subject with protocol-mandated procedures
- Withdrawal of consent by subject
- Physician (Investigator) Decision
- Lost to Follow-Up
- Study is terminated by the Sponsor

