5.0 OVERALL STUDY DESIGN AND PLAN

5.1 Study Design

[figure not shown]
This is a multicenter, open-label, Phase 2 study of NKTR-102 in subjects with solid tumors who received NKTR-102 in a prior Nektar-sponsored clinical study. Following completion of NKTR-102 treatment on a prior NKTR-102 clinical study, subjects will be assessed for eligibility. The Sponsor must approve enrollment of all subjects.

Eligible subjects will continue treatment with NKTR-102 at a dose of 145 mg/m² or less in a q21d schedule as outlined in Figure 1: Study Schematic. Subjects who previously received a dose of NKTR-102 at <145 mg/m² will continue at the lower dose in this study. Subjects who underwent dose reduction of NKTR-102 due to observed toxicity prior to participation in the Extension study (Protocol 11-PIR-09) will not be re-escalated to the previous dose level upon resolution of the toxicity. Dose escalation for NKTR-102 is not permitted.

NKTR-102 will be administered as an IV infusion over approximately 90 minutes (± 15 minutes) on Day 1 of each 21-day treatment cycle.

Subjects will continue to receive repeated cycles of NKTR-102 treatment until disease progression, unacceptable toxicity, death, withdrawal of consent by the subject, Principal Investigator decision, subject non-compliance, lost to follow-up, or study is terminated by the Sponsor. After discontinuation of NKTR-102, all subjects, except those who withdraw consent from further study follow-up, are to be followed for disease status (as applicable), subsequent anti-cancer therapy, survival status, and resolution of toxicity attributable to study drug (with contact by phone, through a clinic visit, or through review of medical records at least every 3 months) until death.

Figure 1: Study Schematic

a Pre-treatment safety assessments and NKTR-102 administration will occur on Day 1 of each cycle.

b Tumor assessments will be performed as required by standard of care.

c Treatment cycles will be repeated until disease progression, unacceptable toxicity, death, withdrawal of consent by the subject, Principal Investigator decision, lost to follow-up, or study is terminated by Sponsor (See Section 5.1).

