7.6 Efficacy Analysis

Tumor response will be assessed by the investigator according to the frequency that patient's standard of care allows. Baseline will be the assessment at screening visit. Data on the best response and disease progression (per physician assessment) will be collected according to RECIST criteria version 1.1 (Eisenhauser et al., 2009). Tumor assessment and responses at the baseline and subsequent visit will be presented in a listing. Best overall response (BOR) by investigator assessment will be summarized. Time to progression and survival time will be calculated from first dose of original NKTR-102 study enrollment. Time to progression is defined as time from date of first dose of original NKTR-012 study to the 1st date of progressive disease (PD) per investigator assessment in current study. Patients without PD will be censored in last visit/follow-up date. Time to death is defined as time from date of first dose of original NKTR-102 study to death date. Patients without death date will be censored in last visit/follow-up date.

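### An undefined physician decision can end survival follow-up under Protocol 7.4, 10.0 and Appendix 1 note k, although 4.2 exempts only subjects who withdraw consent; those subjects are then censored

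*Protocol*

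**What the plan says.** **Who is followed.** Protocol 4.2, with the same rule in the synopsis, says that after NKTR-102 stops "all subjects, except those who withdraw consent from further study follow-up, are to be followed for disease status (as applicable), subsequent anti-cancer therapy, survival status". Drug-related toxicity is tracked as well. Withdrawal of consent to follow-up is the only exception.

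**When follow-up ends.** Protocol 7.4: "Quarterly follow-up will continue until death, withdrawal of consent by subject, physician decision, lost to follow-up, or the study is terminated by the Sponsor". Section 10.0 and Appendix 1 note k give the same list. None of the three says what counts as a physician decision or asks for a reason. Section 7.4 also says that progression ends the assessment of disease status; it does not list progression as an end of follow-up.

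**Leaving the study.** Protocol 5.3: "Subjects may stop NKTR-102 treatment or be withdrawn from the study for any of the following reasons, but will be followed for safety until resolution" of toxicity. The single list that follows includes progression, adverse event, non-compliance and investigator decision. The same section calls survival status an objective.

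**Recovery of missing deaths.** Protocol 5.3.1 asks the investigator, when a subject withdraws from treatment, to make every effort to learn whether follow-up (survival included) may continue. It allows a public-records mortality check, where lawful, for subjects lost to follow-up or who withdrew consent.

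**Analysis.** SAP 5.1 has the consent-only exception, with contact "at least every 3 months) until death". SAP 7.6 measures time to death from first dose in the original study and adds: "Patients without death date will be censored in last visit/follow-up date".

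**The concern.** The protocol gives two rules for the same activity. A site that closes a subject on physician judgement complies with 7.4 and breaks 4.2.

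The other ends of follow-up in 7.4 that 4.2 omits, loss to follow-up and sponsor termination, are ordinary limits. Physician decision differs because it is discretionary and can depend on how the subject is doing. Censoring at last follow-up is valid only if those who leave have the same outlook as those who stay. If subjects are released from follow-up because they are declining, their deaths go unrecorded and survival looks longer than it was. With a single arm, there is no comparator in which the bias could partly cancel.

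At stake is the survival-status part of the secondary objectives (Protocol 3.2, SAP 3.2) and the time-to-death variable in SAP 7.6.

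**Working it through.** **Step 1. Set the rules side by side.** The plan states no rate or figure for this point, so there is nothing to reproduce.

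| Event after treatment stops | Protocol 4.2 | Protocol 7.4, 10.0, App. 1 note k | 5.3.1 records check |
|---|---|---|---|
| Consent to follow-up withdrawn | exempt | ends follow-up | covered |
| Lost to follow-up | not mentioned | ends follow-up | covered |
| Sponsor terminates study | not mentioned | ends follow-up | not covered |
| Physician decision | not exempt | ends follow-up | not covered |
| Progression | not exempt | does not end follow-up | not applicable |

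Physician decision is the only discretionary row in which follow-up ends, 4.2 gives no exemption, and the records check gives no recovery.

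**Step 2. Trace such a subject into the analysis.** No death date is recorded, so SAP 7.6 censors at last follow-up. The rule is the same whatever the reason for exit, and the section plans no sensitivity analysis by reason.

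**Step 3. Is a link with prognosis plausible?** Protocol 2.1.2.5 discusses physician-decision withdrawals from treatment in the Phase 3 study: 28/429 = 6.5% on NKTR-102 and 57/423 = 13.5% on the comparator. In that context it names general deterioration and reduced performance status as typical reasons for clinical progression. These are treatment withdrawals in another study. They make the link plausible but do not give a rate of exit from follow-up.

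**Step 4. Direction and size, as an illustration only.** Assumptions:
- Survival T is exponential with median 10.3 months, so the hazard is ln 2/10.3 = 0.067 per month. The median is that of the Phase 2 breast cancer study in Protocol 2.1.2.2.
- A share f of subjects leaves a fixed lead L before death and is censored at T − L (or at 0.01 months if T is shorter than L).
- Administrative censoring is at 36 months. The simulation has 400,000 subjects.

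Apparent Kaplan-Meier median in months:

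| Share f | L = 1 | L = 3 | L = 6 |
|---|---|---|---|
| 0 | 10.3 | 10.3 | 10.3 |
| 6.5% | 10.9 | 10.9 | 10.8 |
| 13.5% | 11.8 | 11.6 | 11.3 |
| 20% | 12.7 | 12.4 | 12.0 |
| 30% | 14.4 | 13.9 | 13.2 |

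Hand check: as L approaches 0, each death is recorded with probability 1 − f, so the apparent median tends to 10.3/(1 − f). That is 10.3/0.935 = 11.0 at 6.5% and 10.3/0.70 = 14.7 at 30%. The L = 1 column lies just below these limits, as it should.

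With L = 3, 12-month survival reads 46.5% at f = 6.5% and 54.9% at f = 30%. The true value is 0.5^(12/10.3) = 44.6%.

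**Step 5. Control.** When the same shares are censored independently of prognosis, the median stays at 10.3. The bias therefore comes from the dependence on prognosis, not from the amount of censoring.

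**The case against.** - **Sections 4.2 and 7.4 do different jobs.** One says who enters follow-up and the other when it ends; 4.2 also omits loss to follow-up and sponsor termination, so it is not a full list of end reasons. The ending rule is consistent in three places. This explains how the texts arose. It does not explain why a discretionary reason belongs beside the ordinary ones when 4.2 names a single exception.
- **Section 5.3 might be read as removing subjects from survival follow-up at progression.** The documents do not support that. The list mixes stopping treatment with leaving the study, which is loose drafting. But 5.3.1 asks for every effort to secure permission for survival follow-up, and 7.4 ends only disease-status assessment at progression. What stands is an ambiguity.
- **SAP 5.1 may be out of date.** SAP 2.0 says it was written to amendment 2.0 of 25 September 2013, while Protocol 2.1.2.4 reports data as of May 2015. The follow-up until death in SAP 5.1 may be older protocol text. The conflict between 4.2 and 7.4 lies within the current protocol and does not depend on it.
- **Harm is not shown.** No section says whom a physician would release from follow-up, or how often. Reasons unrelated to prognosis would leave the estimate unbiased. This stands, and it limits the claim to direction under a condition.
- **The illustration describes no planned statistic.** SAP 7.6 defines time to death and its censoring but names no Kaplan-Meier median, and Protocol 12.2 puts other data into by-subject listings. The 10.3 months come from one tumour type, whereas this study takes mixed solid tumours without progression. This stands too.

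**Conclusion.** The point holds as an inconsistency in the current protocol that opens a discretionary route to informative censoring. If physician-decision exits track decline, time to death is biased upward. The documents give no rate of such exits, so the size is unknown.

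A reader might infer from the table that reported survival will be inflated by a stated number of months. That does not follow: the exit shares and lead times are assumed, and the median is borrowed from another population.

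Consequences are limited. Survival is a descriptive secondary objective in an access study, and SAP 6.1 calls for no hypothesis test or specific sample size, so no error rate, power or enrolment figure changes. The correction is still worth making because it is specific and nearly free.

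**What to change.** 1. Delete physician decision as a reason to end survival follow-up in Protocol 7.4, 10.0 and Appendix 1 note k.
2. State in 5.3 that its list governs stopping treatment, and that survival follow-up ends only on death, withdrawal of consent to follow-up, loss to follow-up or sponsor termination.
3. Extend the public-records check in 5.3.1 to every subject without a recorded death, where law permits.
4. Align the follow-up text in SAP 5.1 with the current protocol.

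The cost is protocol and SAP wording, plus record reviews every 12 weeks for a few more subjects. No visit is added and no treatment rule changes.
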